A. Description of the of the procedures for the double blind placebo controlled arm

Day 1) Phone screening

During an initial telephone conversation, we will provide a brief description of the study, do an initial screening of the subject to ensure that they meet inclusion criteria and do not possess any of the exclusion criteria, and schedule the subject's intake session.

Day 2) Intake session

Subject comes to The John B Pierce Laboratory where written informed consent will be obtained. The subject will be asked to refrain from alcohol use the day before any session. The subject then completes a subset of the following intake measures to determine eligibility:

A. Toxicology/pregnancy screening

We will perform the following screens:

- i. Breath alcohol levels will be assessed with the Alcohawk Elite Breathalyzer.
- ii. Urine toxicology screens will be conducted using the Integrated E-Z Split Key Cup II (Innovacon Inc., San Diego, CA) for opiates, cocaine, THC, PCP and barbiturate.
- iii. We do not wish to study females who may be pregnant. Therefore, all females of childbearing potential will be given a urine pregnancy test.

If a subject tests positive on any of these screens they will be informed of the result and excluded from further participation in the study. The results from these tests will not be recorded for subjects who are excluded for positive results.

Genotyping:

We will collect a saliva sample to genotype for SNPs related to dopaminergic and opiate signaling in the brain. The gene loci tested and their SNPs are attached.

Iowa Gambling Game:

Iowa Gambling Task³¹: Designed to evaluate the ability to postpone immediate reward for a longer-term successful outcome, tests emotional decision-making ability. Subjects play a card game under conditions of limited knowledge about reward and penalty. The participant is presented with 4 decks of card. Two decks are advantageous (A and B); A and B do not give big gains but do not lead to losses after 100 draws. Two decks are disadvantageous (C and D). C

and D give big gains but end up leading to big losses after 100 draws. Patients with inability to delay immediate gratification to improve long-term outcomes perform badly on this task. The gains and losses will be in fake Monopoly money.

Effort Expenditure for Rewards (EEfRT)

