- Upon arrival to the Magnetic Resonance Research Center (MRRC) participants a urine drug test will be obtained as well as Breath alcohol levels will be assessed with the Alcohawk Elite Breathalyzer. If any of these tests are positive the study will be cancelled. Next, vitals signs (VS)(blood pressure, heart rate, respiratory rate, pulse oximetry, and temperature). If the urine drug test is positive for opiates or methadone the study will be cancelled and the subject disqualified for this study.
- Participants with BP < 90/60 and/or heart rate < 60 will be excluded and the study will be cancelled. VS will be logged in to a VS sheet and kept with the participant paper record in our study binders. Mental and neurologic status will be assessed for a baseline using the National Institutes of Health (NIH) Stroke Scale Neurological Assessment flow sheet (see attached form).
- 3. Next 20 ml of blood will be withdrawn. All blood samples will be placed in pre-chilled test tubes, and centrifuged at 4 C and the plasma stored at -70 C until analyzed according to standard procedures in the YCCI Core Laboratory
- 4. Next, participants will be undergo fMRI scanning: fMRI session: Set up is as above for fMRI simulator in fMRI training. Prior to getting the subject into the MR-room all people involved with the study walk through a detector designed to detect metal objects. We will use a Siemens 3T Trio TIM scanner with a 32channel head-coil. A T1-weighted 3D MPRAGE sequence (4 minutes) will be performed to obtain a high-resolution anatomical image and echoplanar imaging will be used to measure

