the BOLD signal as an indication of cerebral activation in response to various tastes (milkshake and tasteless) during two 9.6-minute runs and in response to sucrose and tasteless during two 9.6-minute runs. A run consists of multiple blocks of taste (milkshake or tasteless). One block is a series of 4 - 8 presentations of tastes or tasteless; Each presentation starts with a 0.75 cc delivery of liquid over 2 s followed by 7 s in which to swallow. Each taste block is followed by a rinse (0.75 cc deionized water). Before the start of a new block there is a rest period of 10 seconds. Blocks vary in length between 32 and 80 seconds and the order of blocks is counterbalanced across subjects. This design is modified from prior event-related designs so as to yield a 61% improvement in design efficiency (calculated by FMRIB's software library FSL), which we confirmed to lead to more extensive and more intense BOLD response. The data can be analyzed offline and used for experimental control variables. Next, two 6 minutes resting state runs will be collected. During these runs, participants will be asked to stare at a cross-hair on the screen. Finally, a diffusion tensor imaging (DTI) scan will be obtained over 5 minutes.

5. Participants will be then taken out of the scanner and given one oral dose of either 30 mg of Morphine, or 50 mg of Naltrexone or placebo. 60 minutes later, VS will be collected again and logged in to the VS sheet and participants will undergo another scanning session while receiving milkshake, sucrose or tasteless solutions as described in 3 and while at rest. DTI and structural imaging will not be repeated. Blood pressure and heart rate will be continuously monitored during scanning using the Biopac system. The same procedure will be followed for the same participants in two subsequent visits (Day 4 and Day 5). *The*

Figure 1. Schematic illustration of study design; the order is just one example for one participants; the interventions will be randomized in a double blind protocol.

visits will be scheduled within a period spanning 4 weeks but no two-treatment days will be scheduled less than 48 hours apart. The overall design of the study will follow the illustration in Figure 1. However, the order of the interventions (i.e. Morphine, Naltrexone or placebo) will be randomized. The scanning session after medication administration will last between 45-60 minutes. Participants vital signs and mental

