and neurological state will be monitored for an additional 2 hours post-scanning at an interval of one hour using the NIH Stroke Scale Neurological Assessment flow sheet (two assessments in total); after 2 hours, if participants mental and neurologic state and VS are stable they will be reminded about side-effects of morphine and naltrexone and released. Morphine sulfate half-life is 2-4 hours. By the time our participants leave the MRRC one to two half-lives would have passed and the blood level of morphine would have dropped 2 to 4 times relative to time at ingestion.

B. Description of the open label arm

The same procedures described in A will be used to study 15 CBP patients using an open label design except when participants are taken to the scanner. At that point both the experimenter and the participant will know that morphine 30 mg is being administered. In addition, this arm of the study will have one arm only.

4. Genetic Testing N/A

A. Describe

i. the types of future research to be conducted using the materials, specifying if immortalization of cell lines, whole exome or genome sequencing, genome wide association studies, or animal studies are planned.

No future research is planned with the materials. We will determine the presence or absence of candidate opiate activity-related genes after the subject has provided their saliva.

ii. the plan for the collection of material or the conditions under which material will be received

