The subjects will be healthy human adults, and human adults suffering from pain conditions such as low back pain, knee arthritis, or fibromyalgia with normal gustatory and olfactory function and no medical conditions that would preclude them from being tested in the MR scanner. These subjects will be recruited from the Yale University Community, including undergraduate students, graduate students, and staff, with an age range between 18 and 65 years. Women and minorities will be encouraged to participate in all proposed experiments. We will monitor the subject pool periodically to ensure appropriate representation of all ethnic backgrounds and both sexes.

6. **Subject classification:** Check off all classifications of subjects that will be specifically recruited for enrollment in the research project. Will subjects who may require additional safeguards or other considerations be enrolled in the study? If so, identify the population of subjects requiring special safeguards and provide a justification for their involvement.

Children	🔀 Healthy	Fetal material, placenta, or dead fetus
Non-English Speaking	Prisoners	Economically disadvantaged persons
Decisionally Impaired	Employees	Pregnant women and/or fetuses
Yale Students	Females of ch	nildbearing potential

NOTE: Is this research proposal designed to enroll children who are wards of the state as potential subjects? Yes No (If yes, see Instructions section VII #4 for further requirements)

 Inclusion/Exclusion Criteria: What are the criteria used to determine subject inclusion or exclusion? Inclusion criteria:

NCT04342130

Healthy participants

Patients in pain: suffering from persistent pain more days than not, 3/10 in intensity on a numerical rating scale, for at least 6 weeks or more.

Exclusion criteria: Any DSM diagnosis, diabetes, food allergies, lactose intolerance, participants seeking to quit smoking or to lose weight, participants on any psychotropic medication including opiate based analgesics (e.g. oxycodone, methadone, suboxone), pregnant or nursing women, pacemaker or other implanted electrical devices. Participants with a past history of head trauma or seizures will be excluded. Any past history of illegal drug or alcohol misuse will be an exclusion criterion.

8. How will **eligibility** be determined, and by whom?

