During the fMRI scans, the participants will be monitored for anxiety or related concerns by research personnel associated with the project. Participants and investigators will be screened for metallic objects prior to entering the scan room. Prior to inclusion in the study, the presence of potential MRI risks, such as pacemakers, surgical clips, or metallic devices will be excluded by medical and surgical history administered during screening. All subjects will wear foam earplugs and sound-reducing headphones to reduce risk of hearing damage due to the loud noise of the scanner. The minor risk of discomfort due to lying still for 60 minutes will be minimized by providing custom pads and pillows designed to make the participants as comfortable as possible. Participants will communicate with the MR technologist and research assistant via an intercom system and may trigger and audible alarm at any time to stop the MRI session if he or she is uncomfortable or anxious. In addition, all imaging center staff, students, post-docs and research assistants will participate in safety training annually. Finally, all subjects are familiarized with MR procedures during the training session in the mock scanner to ensure that subjects that are schedule for the MR scan are comfortable with the procedures.

Minimizing risks related to pregnancy

To minimize risks related to pregnancy, we inform the subject that if they should become pregnant, they should report this to their health care professional, physician and to us immediately. If this happens during the study, the subject will stop his/her participation. We perform pregnancy tests along with toxicology tests during each assessment and intake.

Minimizing risks associated with the BodPod

The experimenter can see the subject at all times in the BodPod and will show them the alarm button inside the BodPod that will interrupt the measurement if they feel anxious.

Minimizing risks for toxicology screenings:

Every subject will use a new separately wrapped mouthpiece that will be attached to the breathalyzer. Bottles containing subject's urine specimens will be not be labeled and will be appropriately discarded in a biohazard container after instant testing. This information is not recorded.

Minimizing risks for saliva sample collection and genotyping:

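### In the double-blind arm, the opiate-positive disqualification rule makes no allowance for the study's own morphine at Days 4 and 5 (minor, cheap to fix)

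*Combined protocol and SAP*

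**What the plan says.** On arrival at the Day 3 scan session (Section V, item 3, Research Plan, part A), urine drug and breath alcohol tests are taken. Any positive cancels the session. Opiates and methadone carry a heavier, permanent consequence: "If the urine drug test is positive for opiates or methadone the study will be cancelled and the subject disqualified for this study".

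Step 5 of that session gives one oral dose of morphine 30 mg, naltrexone 50 mg or placebo, and ends by extending the session to later days: "The same procedure will be followed for the same participants in two subsequent visits (Day 4 and Day 5". On spacing: "visits will be scheduled within a period spanning 4 weeks but no two-treatment days will be scheduled less than 48 hours apart". On sequence: "However, the order of the interventions (i.e. Morphine, Naltrexone or placebo) will be randomized". Section V, item 10 (Minimizing Risks, under pregnancy) adds: "We perform pregnancy tests along with toxicology tests during each assessment and intake".

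The rule supports the exclusion in Section V, item 7 of "participants on any psychotropic medication including opiate based analgesics (e.g. oxycodone, methadone, suboxone". The only screening product named is the one used at intake: "Urine toxicology screens will be conducted using the Integrated E-Z Split Key Cup II". Its listed panel includes opiates but not methadone. No cut-off or detection window is stated for any urine screen. The only pharmacokinetic figure is "Morphine sulfate half-life is 2-4 hours", which the protocol uses to discuss blood level at release.

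Two places limit record keeping. The intake section says results are not kept for people excluded on a positive screen. Item 10, under toxicology screenings, says the screening information is not recorded.

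**The concern.** The rule is meant to keep out people who take opiates from outside the trial. From Day 4 onward, however, a participant may have taken an opiate because the trial gave it. The text does not distinguish the two sources and does not say how a positive after an earlier study dose should be handled under the blind.

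Disqualification for outside opiate use does not depend on treatment order. Disqualification caused by study morphine does: it can occur only when morphine is given at the first or second visit. The analysis in Section V, item 12 compares the three treatments within the same person, so each such loss removes one or more paired comparisons, and the orders among completers become unequal. Because screening results are not recorded, the cause of these losses might also never be visible in the data.

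**Working it through.** **Plan's own figure.** The protocol says blood morphine falls 2 to 4 times by release. Dose to release is 1 h wait + 0.75 to 1 h scan + 2 h observation = 3.75 to 4 h. With fold drop = 2^(t / half-life), 2^(3.75/4) = 1.9 and 2^(4/2) = 4.0. This agrees, so the same formula is used below.

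**Does the rule carry to Days 4 and 5?** Step 5 repeats the procedure at two later visits, and item 10 says toxicology is done at each assessment. Together they place an opiate screen before each later dose. No text exempts a prior study dose.

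**Which orders are exposed?** M = morphine, N = naltrexone, P = placebo. Suppose the test at the visit after morphine is positive:

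| Order | Visits completed | Pairs lost |
|---|---|---|
| M-N-P | M | M-P, M-N, N-P |
| M-P-N | M | M-P, M-N, N-P |
| N-M-P | N, M | M-P, N-P |
| P-M-N | P, M | M-N, N-P |
| N-P-M | all | none (no later test) |
| P-N-M | all | none (no later test) |

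So 4 of 6 orders are exposed. Within those four, M-P is lost in 3, M-N in 3 and N-P in 4.

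**What does the half-life suggest at 48 h?**
- 4 h half-life: 48/4 = 12 half-lives; 30 mg x 2^-12 = 7.3 micrograms.
- 2 h half-life: 48/2 = 24 half-lives; 30 mg x 2^-24 = 0.0018 micrograms.

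This points to a low rate. It describes parent drug in blood and cannot be converted to a urine result without a cut-off or window, which the documents do not give.

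**Expected loss over an assumed range.** Target enrolment is 75 (Section VII, item 1) and the open-label arm has 15 (Section V, item 3, part B). Assume that the 75 includes the 15 and that the six orders are equally used. Then the double-blind arm has 75 - 15 = 60, of whom 60 x 4/6 = 40 are tested after morphine. For an assumed chance q of a positive at the next visit, loss L = 40q. If only completers are analysed, with unchanged variance per person, the standard error is multiplied by sqrt(60/(60 - L)). The 20 with morphine last are untouched, so their share of completers is 20/(60 - L).

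| q (assumed) | Lost of 60 | SE multiplier | Share with morphine last |
|---|---|---|---|
| 0% | 0 | 1.000 | 20/60 = 33.3% |
| 5% | 2 | 1.017 | 20/58 = 34.5% |
| 10% | 4 | 1.035 | 20/56 = 35.7% |
| 25% | 10 | 1.095 | 20/50 = 40.0% |

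**The case against.** The strongest reply is that no loss is demonstrated. Everything depends on a urine screen still detecting study morphine at the chosen gap, and nothing in the documents establishes that. The one relevant figure, the half-life, suggests it would be uncommon. The 48 hours is also a minimum: two equal gaps in a 28-day window would be 14 days each. This stands, and it is why the point is minor and the range above starts at zero.

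Second, the repeat instruction follows directly after dosing and rescanning, so it could be read as repeating only that step. Item 10 confirms repeat toxicology without restating disqualification. The narrow reading is possible but less natural, and it would leave no stated action for an opiate-positive before a Day 4 or 5 dose. Clarifying text is useful under either reading.

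Third, the rule is a defensible safeguard against giving morphine or naltrexone to someone who already has opiates on board. That is accepted, and the fix keeps it.

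A reader might infer that a different product is used on scan days, because the scan-day rule covers methadone and the intake panel does not. Loose wording explains the mismatch equally well. The missing cut-off is likewise an absent detail that the named product's label may supply, not an error in the plan.

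**Conclusion.** The gap in the text is real, limited to the double-blind arm, and minor. As most naturally read, a stated rule could permanently remove participants because of the trial's own drug, and only in the 4 of 6 orders with morphine first or second. At assumed positive rates of 0%, 5%, 10% and 25%, the loss is about 0, 2, 4 and 10 of 60. This rests on balanced orders (the protocol says only that order is randomised) and on the 75 including the 15 open-label patients. The true rate is unknown and probably low.

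A reader might go further and infer that the drug contrast is biased. The documents do not support that. Order is randomised, the rate is unknown and may be zero, no visit effect is quantified, and the statistical section does not say how the repeated measures ANOVA treats incomplete participants. What can be said is that any such loss costs within-subject data and unbalances the orders among completers.

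**What to change.** Either or both of these changes, in the double-blind arm:

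- **Longer gap (preferred).** Raise the minimum between treatment days above 48 hours, ideally beyond the detection window on the label of the screen used. Seven days is an example: 168/4 = 42 to 168/2 = 84 of the stated half-lives, using 2 x 7 = 14 of the 28 days allowed.
- **Retest before disqualifying.** For every participant regardless of allocation, an opiate-positive at Day 4 or 5 cancels the visit with no dose given and the visit is rescheduled. Only a positive retest disqualifies. The code-holder is not consulted, because acting on the answer would unblind those who continue.

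A coded reason should be logged for each cancellation and kept from staff who score or analyse the scans.

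The cost is about two protocol sentences and one log field. The log must be reconciled with both non-recording statements, at intake and in item 10. Scheduling becomes longer. Retesting alone, with 48-hour gaps and 7-day reschedules of both later visits, needs 2 + 7 + 2 + 7 = 18 days. With 7-day gaps as well, it needs 4 x 7 = 28 of 28 days and leaves no slack. Retesting also carries a small chance of keeping a one-off outside opiate user, and a positive followed by a negative retest is a weak clue to earlier morphine. The longer gap avoids both, which is why it is preferred.

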fMRI Data Analysis: The following measures will be derived from brain data: (1) parameter estimates(PE) for milkshake (MS) minus Tls (tasteless) (MS-Tls) will be defined at the single subject level using general linear model (GLM), implemented in FSL toolbox⁵⁵; whole brain connectivity of Blood Oxygen Level Dependent (BOLD) signal, using both MS runs or resting state runs, will be calculated between each voxel, or region of interest (ROI), and every other voxel in the brain to obtain (2) functional connectivity *FC* of specific ROIs or (3) degree maps (DM). *FC* is a measure of the strength of connectivity between an ROI and the rest of the brain; degree *D* is calculated as the total number of connections above a specific correlation threshold between a voxel and all the other voxels in the brain; we will study *D* over a range of thresholds 0.25 < r < 0.65 ⁵⁶. *DM* identifies brain hubs (with high *D*) and therefore allows between groups comparison in the most densely connected areas ^{57,58}.

The design is a within subject repeated measures design with treatment (Morphine, Naltrexone and Placebo) being the repeated measure and groups (healthy control vs. pain patients) as a factor. We will use repeated measures ANOVA to find differences in brain response (i.e. (*MS-Tls*) or *D* or *FC*) and psychophysical ratings of milkshake. The repeated measures design is a powerful one because it does not suffer from between subject

NCT04342130

variability. According to the preliminary data we expect to see decreased response to MS in opiate treated back pain patients and decreased D and FC.

SECTION VI: RESEARCH INVOLVING DRUGS, BIOLOGICS, RADIOTRACERS, PLACEBOS AND DEVICES

If this section (or one of its parts, A or B) is not applicable, state N/A and delete the rest of the section.

A. DRUGS, BIOLOGICS and RADIOTRACERS

1. **Identification of Drug, Biologic or Radiotracer:** What is (are) the **name(s)** of the drug(s) biologic(s) or radiotracer(s) being used? Identify whether FDA approval has been granted and for what indication(s).

- Morphine has U.S. Food and Drug Administration (USFDA) approval for relief of moderate to severe acute and chronic pain for which use of an opioid analgesic is appropriate.
- Naltrexone has USFDA approval for treatment of alcohol dependence and blockade of the effects of exogenously administered opioids.

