- Hematologic & oncologic: Anemia (2% to <5%), thrombocytopenia (<2% to <5%), leukopenia (2%), hematocrit decreased
- Hepatic: Increased liver function enzymes
- Hypersensitivity: Hypersensitivity reaction
- Infection: Infection
- Local: Local irritation
- Neuromuscular & skeletal: Back pain (<2% to 10%), asthenia (2%), tremor (2%), arthralgia (<2%), bone pain (<2%), foot-drop (<2%), decreased bone mineral density, muscle rigidity, muscle twitching
- Ophthalmic: Amblyopia (<2%), blurred vision (<2%), conjunctivitis (<2%), diplopia (<2%), miosis (<2%), nystagmus (<2%), eye pain, visual disturbance
- Respiratory: Dyspnea (3% to 10%), flu-like symptoms (<2% to 10%), hypoventilation (<5%), asthma (<2%), atelectasis (<2%), hypoxia (<2%), pulmonary edema (noncardiogenic, <2%), respiratory depression (<2%), respiratory insufficiency (<2%), rhinitis (<2%), hypercapnia
- Miscellaneous: Accidental injury (2% to 10%), fever (2% to 10%)

Side effects at < 1%

• <1% (Limited to important or life-threatening): Anaphylaxis, apnea, biliary tract spasm, bronchospasm, decreased cough reflex, dehydration, disorientation, disruption of body temperature regulation, genitourinary tract spasm, hemorrhagic urticaria, hyperalgesia, hypertonia, increased intracranial pressure, intestinal obstruction, laryngospasm, menstrual irregularities, myoclonus, paradoxical central nervous system stimulation, sepsis, toxic psychoses

Oral Morphine is contraindicated in somebody who has bowel obstruction.

Oral Naltrexone: Oral Naltrexone is prescribed for alcohol and opiate dependence; it is estimated that 221 million prescriptions of Naltrexone were dispensed in 2007⁷⁴. The starting dose is 50 mg daily. Naltrexone has a wide margin of safety. Naltrexone has a low incidence of common adverse events⁷⁵. Naltrexone's FDA-approved label includes a black-box warning regarding hepatotoxicity, although these reversible effects tend to be associated with much higher doses than those used in routine clinical practice (e.g., 300 mg/day or more) and tend to occur only after a patient is on these high doses for extended periods. *For the purpose of our current protocol we will use one 50 mg dose one time only.* In addition, there is no evidence of long-term toxicity associated with the intake of one dose of Naltrexone. Naltrexone side effects occurring at > 10% rate are reported for combined oral and injectable form; however, as mentioned above oral Naltrexone has a low risk of side effects.

>10%:

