Did the FDA approve this IDE as **Category A** (experimental/investigational) or as **Category B** (non-experimental/investigational)?

Who holds the IDE?

Non-Significant Risk (NSR) Device Study: A study of a device that does not meet the definition for a significant risk device and does not present a potential for serious risk to the health, safety, or welfare of participants. Note that if the HIC concurs with this determination, an IDE is not required.

6. Abbreviated IDE or Exempt IDE: There are abbreviated requirements for an IDE and there also are exemptions to the requirement for an IDE. See the criteria in the HIC Application Instructions, Section VI.B.4 at http://www.yale.edu/hrpp/resources/docs/100FR1aHICProtocol_Application_Instructions5-25-11.pdf to determine if these pertain to this study.

Abbreviated IDE or Exempt IDE – *If criteria set forth in the HIC Application Instructions are met, copy and paste the completed relevant section from the Instructions into this application.*

7. Investigational device accountability:

a. State how the PI, or named designee, ensures that an investigational device is used only in accordance with the research protocol approved by the HIC, and maintains control of the investigational device as follows:

Maintains appropriate records, including receipt of shipment, inventory at the site, dispensation or use by each participant, and final disposition and/or the return of the investigational device (or other disposal if applicable):

Documents pertinent information assigned to the investigational device (e.g., date, quantity, batch or serial number, expiration date if applicable, and unique code number):

Stores the investigational device according to the manufacturer's recommendations with respect to temperature, humidity, lighting, and other environmental considerations:

Ensures that the device is stored in a secure area with limited access in accordance with applicable regulatory requirements:

Distributes the investigational device to subjects enrolled in the IRB-approved protocol:

SECTION VII: RECRUITMENT/CONSENT AND ASSENT PROCEDURES

1. Targeted Enrollment: Give the number of subjects:

a. targeted for enrollment at Yale for this protocol_75

b. If this is a multi-site study, give the total number of subjects targeted across all sites____

2. Indicate recruitment methods below. Attach copies of any recruitment materials that will be used.

3. Recruitment Procedures:

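### The three-visit crossover is analysed by treatment and group with no visit-period term, which gives away some precision that one extra factor would recover

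*Combined protocol and SAP*

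**What the plan says.** Section V, 3. Research Plan (Day 3 fMRI scan session) describes three treatment visits for the same participants, one each for morphine, naltrexone and placebo. It states that "the order of the interventions (i.e. Morphine, Naltrexone or placebo) will be randomized". It does not mention balanced sequences or a Latin square. On timing, "visits will be scheduled within a period spanning 4 weeks but no two-treatment days will be scheduled less than 48 hours apart". At every visit a taste and resting-state scan comes before the dose, and a second one starts 60 minutes after it.

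Section V, 12. Statistical Considerations specifies a repeated measures ANOVA of brain response and milkshake ratings, "with treatment (Morphine, Naltrexone and Placebo) being the repeated measure and groups (healthy control vs. pain patients) as a factor". No other factor is named. The section does not say whether the outcome is the post-dose scan or the change from the pre-dose scan. It defends the design on efficiency: "The repeated measures design is a powerful one because it does not suffer from between subject" variability.

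Section VII, 1 gives the enrolment as "targeted for enrollment at Yale for this protocol_75". Section V, 3.B describes 15 open-label back pain patients and does not say whether they are among the 75.

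**The concern.** Each participant has six taste-scan sessions (two per visit, three visits) with the same stimuli. Response to a repeated taste, and comfort in the scanner, could well change from the first visit to the third. In a crossover such a change is a period effect. Randomizing the order spreads it across the three treatments but does not remove it from the data.

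A model with only participant, treatment and group has nowhere to put it except the error term. If the orders happen to be balanced, the treatment estimates are unaffected but their reported standard errors are too wide. If the orders are simply randomized, the estimates are themselves noisier, because chance imbalance between treatment and visit goes uncorrected. In both cases the plan loses part of the power on which it justifies the design.

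**Working it through.** The plan gives no power calculation, SD, effect size or expected visit trend, so there is no figure of its own to reproduce.

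**Inputs**
- Visits and treatments: three of each (Section V, 3).
- Crossover participants: 75 − 15 = 60, assuming the open-label patients are within the 75.
- Within-participant SD: set to 1, so everything is in SD units.
- Drift: linear, d per visit, assumed at 0.25 to 0.5 SD. The documents give no value.

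**Standard error**
1. With no drift, a participant's morphine-minus-placebo difference has variance 1 + 1 = 2.
2. Over the six possible orders, the squared number of visits between morphine and placebo averages (1+4+1+1+4+1)/6 = 2, so drift adds 2d².
3. Without a period term the variance is 2 + 2d², so the error variance is multiplied by 1 + d² and the standard error by √(1 + d²).
4. At d = 0.25, √1.0625 = 1.031, which is 3% wider. The equivalent sample is 60/1.0625 = 56.5.
5. At d = 0.5, √1.25 = 1.118, which is 12% wider. The equivalent sample is 60/1.25 = 48.
6. The ratio does not depend on the sample size. If the 15 are additional to the 75, the widening is unchanged and the equivalents are 75/1.0625 = 70.6 and 75/1.25 = 60.

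**Simulation.** 60 participants, an assumed treatment effect of 0.5 SD, two-sided 5% level, 1,500 runs per setting. Each cell shows the result without the period term, then with it.

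| Drift per visit | Orders | Power | Type I error | SD of estimate |
|---|---|---|---|---|
| 0 | balanced | 0.775 / 0.777 | 0.044 / 0.043 | 0.187 / 0.187 |
| 0 | simple | 0.783 / 0.777 | 0.059 / 0.060 | 0.182 / 0.183 |
| 0.25 | balanced | 0.743 / 0.767 | 0.046 / 0.048 | 0.185 / 0.185 |
| 0.25 | simple | 0.755 / 0.774 | 0.052 / 0.046 | 0.188 / 0.185 |
| 0.5 | balanced | 0.712 / 0.782 | 0.032 / 0.056 | 0.182 / 0.182 |
| 0.5 | simple | 0.685 / 0.770 | 0.049 / 0.052 | 0.206 / 0.187 |

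Simulation error on a power figure is about √(0.75 × 0.25/1500) = 0.011. Leaving period out does not inflate type I error. With balanced orders and the larger drift, the test becomes conservative (0.032). With simple randomization, the estimate itself is more variable (0.206 against 0.187). At zero drift the term costs essentially nothing.

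**Degrees of freedom.** Without period, (60 − 2) × 2 = 116. With period, 114.

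**The case against.** The strongest reply is that this is a refinement of efficiency. Order is randomized, so the comparison is unbiased on average and type I error is not inflated. That stands, and a reader who inferred a biased or invalid treatment comparison from the missing term would be wrong.

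The drift and the 0.5 SD effect are both assumed. At 0.25 SD per visit the power loss is only about 2 points. That also stands. The size is conditional, and only the upper end of the range is material.

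The pre-dose scan at each visit is a real partial safeguard. If post-minus-pre change is analysed, drift common to both scans cancels and the loss shrinks. But Section V, 12 does not put the pre-dose scan in the model, so the protection cannot be assumed.

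The document is an ethics application with a short statistics section, so silence on a covariate is weak evidence that it will be omitted. Against that, the section names a specific model and its factors, and period is not one of them.

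A stronger reading is also tempting: that a 48-hour gap lets naltrexone blunt morphine at the next visit. Naltrexone is described as a blocker of exogenous opioids, and no reason is given for the 48 hours. The documents do not support going further. For morphine, "Morphine sulfate half-life is 2-4 hours", so at most 2^(−48/4) = 0.024% is left at 48 hours. For naltrexone no duration is given. The only clue, "The starting dose is 50 mg daily", suggests about a day, against a 48-hour minimum. With assumed naltrexone half-lives of 4 to 24 hours, visits placed at random in the 28 days and blockade proportional to residual drug, the average morphine effect falls by under 0.001% to 1.3%. A fall of 8.3% (25%/3) needs both a 24-hour half-life and every naltrexone-then-morphine gap at exactly 48 hours.

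**Conclusion.** The point holds as a loss of precision. The stated model leaves visit-to-visit change in the error term of a design chosen for its power. For a linear drift of 0.25 to 0.5 SD per visit, the morphine-versus-placebo standard error is 3% to 12% wider than needed. This rests on the assumed drift, on roughly equal use of the six orders, and on analysing post-dose values. It is smaller for change from pre-dose, and nil if there is no drift. The change is worth making because it costs almost nothing, although no conclusion of the trial is shown to be at risk.

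The 48-hour gap is at most a reporting note. Carry-over is not shown, and a longer minimum is not supported as a required change.

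**What to change.** Add visit period (1, 2, 3) as a within-participant factor to the Section V, 12 model, for both the brain measures and the milkshake ratings. State in the same place whether the outcome is the post-dose scan or post-minus-pre-dose change, since that determines how much the term recovers. The cost is 2 of about 116 error degrees of freedom. It needs no new data and no change to visits.

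Optionally, add one sentence giving the reason for the 48-hour minimum as it applies to naltrexone. The period term would not correct residual blockade if there were any. Raising the minimum to 4 or 7 days is not proposed: it would rule out about 42% or 80% of randomly placed schedules now allowed, from 1 − ((28 − 2m)/24)³ with m = 4 or 7, to guard against an effect that the documents do not show.
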